1.0 Objectives

1.1 Purpose, Objectives, Specific Aims

Our prior work demonstrates that older people with lower extremity peripheral artery disease (PAD) have greater functional impairment and faster functional decline compared to those without PAD (1-4). PAD-related functional limitations are associated with increased healthcare costs and loss of independence (5-10). Yet few medical therapies have been shown to improve functioning or prevent mobility loss in older people with PAD.

People with PAD have impaired endothelial function, impaired calf muscle perfusion, reduced skeletal muscle mitochondrial activity, and reduced calf muscle mass and strength (11-20). Preliminary pre-clinical and human evidence show that cocoa and its major flavanol component, epicatechin, have therapeutic properties that reverse the pathophysiologic impairments that are present in PAD. Specifically, cocoa and epicatechin improve endothelial function, increase skeletal muscle mitochondrial function, increase skeletal muscle angiogenesis, reduce skeletal muscle levels of myostatin, and increase skeletal muscle levels of follistatin (21-31).

Myostatin is a growth differentiation factor that promotes muscle wasting. Follistatin blocks myostatin's action, thereby promoting muscle growth. By reducing myostatin and increasing follistatin, epicatechin-rich cocoa has potential to increase muscle mass and strength (22,25). A small study in humans with type 2 diabetes and heart failure showed that epicatechin-rich cocoa increased skeletal muscle mitochondrial biogenesis, increased mitochondrial cristae abundance, and improved grip strength (25). A small randomized cross-over trial in PAD patients showed that dark chocolate (>85% cocoa), but not milk chocolate (<35% cocoa), acutely increased treadmill walking time, improved endothelial function, and reduced oxidative stress two hours after chocolate ingestion (31). However, no randomized trials have studied whether chronic daily epicatechin-rich cocoa improves walking ability in patients with PAD.

The COCOA-PAD Study is a pilot double-blind, randomized controlled trial to test our hypothesis that epicatechin-rich cocoa improves endothelial function, increases calf skeletal muscle mitochondrial function and biogenesis, and favorably alters skeletal muscle levels of myostatin, follistatin, and mitochondrial transcription factor-alpha (TFAM), thereby improving lower extremity functioning in older people with PAD. If our proposed pilot study supports our hypotheses, results will be used to design a large, definitive randomized clinical trial of epicatechin-rich cocoa in older people with PAD.

Forty-four participants with PAD age 60 and older will be randomized to epicatechin-rich cocoa vs. an epicatechin-free and cocoa-free placebo (matched in appearance and taste) daily for six months. Our primary

outcome is the six-minute walk, a well-validated measure of walking endurance in PAD (32-34). Secondary outcomes are pain-free and maximal treadmill walking performance, brachial artery flow-mediated dilation (FMD), accelerometry-measured physical activity, calf muscle biopsy measures, and MRI-measured calf muscle perfusion. To distinguish between the acute vs. chronic effects of cocoa, the six-minute walk and brachial artery FMD measures will be obtained while off of study beverages for 2.5 hours (acute) and 24 hours (chronic), respectively. . The treadmill stress test will be measured while off of study beverages for 48 hours. Remaining outcomes will be measured while still taking study beverages whenever possible.

Primary Aim. Among 44 participants with PAD age 60 and older, we will determine whether epicatechin-rich cocoa daily for six months improves six-minute walk performance compared to placebo.

Secondary Aims. 1. Among 44 participants with PAD age 60 and older, we will determine whether epicatechin-rich cocoa daily for six months improves maximal and pain-free treadmill walking time, increases brachial artery FMD, and increases accelerometer-measured physical activity compared to placebo. 2. Among 44 participants with PAD age 60 and older, we will determine whether epicatechin-rich cocoa daily for six months favorably improves the following measures obtained with calf skeletal muscle biopsy: activity of Cytochrome C Oxidase (COX) and citrate synthase, calf muscle levels of peroxisome proliferative activated receptor- γ co-activator 1 α (PGC-1 α), capillary density, myostatin, follistatin, and mitochondrial transcription factor-alpha (TFAM), compared to placebo. 3. Among 44 participants with PAD age 60 and older, we will determine whether epicatechin-rich cocoa daily for six months increases calf skeletal muscle perfusion, measured by magnetic resonance imaging (MRI), compared to placebo. 4. Among participants with PAD age 60 and older, we will determine whether epicatechin-rich cocoa daily for six months increases calf skeletal muscle biopsy measures of calf skeletal muscle regeneration and reduces oxidative stress, compared to placebo. Specific measures of calf skeletal muscle regeneration that we will study consist of satellite cell number and activation state and centrally nucleated and embryonic myosin heavy chain-expressing fibers. Specific measures of calf skeletal muscle oxidative stress will be nitrotyrosine and 4-hydroxynonenal (4-HNE).

Exploratory Aims. Among participants with PAD age 60 and older randomized to epicatechin-rich cocoa, we will determine whether the degree of improvement in six-minute walk performance and treadmill walking performance, respectively, is correlated with the degree of improvement in a) calf skeletal muscle perfusion; b) calf skeletal muscle measures of

regeneration; and c) calf skeletal muscle measures of oxidative stress.

1.2 *Hypotheses.*

We hypothesize that:

1. PAD participants randomized to epicatechin-rich cocoa will achieve greater increases in six-minute walk performance at six-month follow-up, compared to those randomized to placebo.
2. PAD participants randomized to epicatechin-rich cocoa will have greater increases in treadmill walking time, brachial artery FMD, and physical activity at six-month follow-up, compared to placebo.
3. Epicatechin-rich cocoa will improve each calf skeletal muscle measure listed above, compared to placebo.
4. PAD participants randomized to epicatechin-rich cocoa will achieve greater increases in MRI-measured calf muscle perfusion at 6-month follow-up, compared to those randomized to placebo.
5. PAD participants randomized to epicatechin-rich cocoa will have more favorable changes in each calf muscle biopsy measure, compared to those randomized to placebo.

2.0 **Background**

2.1 *Relevant prior experience and gaps in current knowledge*

The COCOA-PAD Study builds on our prior work. We have successfully completed large randomized trials of PAD patients. Our prior work demonstrates that people with PAD have greater functional impairment and more rapid functional decline than those without PAD (1-5). The functional impairment in PAD is associated with loss of independence, increased mortality, and poor quality of life (6-10,35).

Few medical therapies are available to improve functional impairment in PAD. Only two medications, pentoxifylline and cilostazol, are FDA-approved for treating PAD-associated walking impairment. Of these, pentoxifylline is usually ineffective and benefits from cilostazol are modest (36-39). New therapies are urgently needed to improve walking performance in patients with PAD.

2.2 *Relevant Preliminary Data.*

A. Calf skeletal muscle fibers and mitochondria are damaged in PAD and contribute to functional decline. Endothelial function is impaired in PAD. First, our work shows that people with PAD have smaller calf muscle area, increased calf muscle fat content, and poorer leg strength compared to people without PAD (19,20,40,41). Greater severity of these calf muscle impairments are associated with greater functional impairment and increased mobility loss in PAD (41-43). Second, electron microscopy

demonstrates pathologic changes in myofibrils, mitochondria, and sarcolemma of calf myofibers in patients with PAD (16,44,45). More severe oxidative stress, such as that associated with walking-related ischemia reperfusion of calf muscle, is associated with more severe myofiber damage (44). Third, PAD patients have reduced calf muscle mitochondrial energy production, measured by reduced adenosine triphosphate (ATP) production, compared to people without PAD (44-50). Lower ATP production is associated with greater functional impairment in PAD (18,44). Fourth, people with PAD have impaired endothelial function compared to people without PAD. Greater endothelial function impairment in PAD is associated with lower physical activity and increased cardiovascular events (11,12,51). Epicatechin-rich cocoa targets all of these pathophysiologic changes that are present in PAD.

B. A5. Pre-clinical evidence suggests that cocoa-derived epicatechin improves skeletal muscle characteristics and vascular function. Epicatechin is a flavanol that exists in high concentrations in cocoa. In pre-clinical studies, epicatechin has therapeutic effects on skeletal muscle. First, Huttelman and colleagues studied 21 rats randomized to one of three groups: Group 1: epicatechin for 30 days; Group 2: epicatechin for 30 days followed by 15 days with no therapy; Group 3: Placebo. At 30 day follow-up, Group 1 had increased skeletal muscle mitochondrial biogenesis and mitochondrial function, measured by increases in PGC-1 α , TFAM, mitochondrial cristae quantity, and capillary density (21). PGC-1 α is a key promoter of mitochondrial biogenesis and mitochondrial function. TFAM increases mitochondrial transcription. Greater mitochondrial cristae provides greater surface area for ATP production. These favorable changes were sustained at 45 day follow-up in Group 2, 15 days after therapy was completed. Second, Gutierrez-Salmean and colleagues administered 1 mg/kg daily of cocoa-derived epicatechin to ten young (6 months old) and ten old (26 months old) mice (22). At two-week follow-up, skeletal muscle levels of myostatin were reduced in the young and older mice by 15% and 21%, respectively, while skeletal muscle levels of follistatin increased by 56% in the older mice (22). Myostatin is a protein and growth differentiation factor that promotes muscle wasting. Follistatin blocks myostatin's action, increasing muscle growth. Thus, cocoa-derived epicatechin achieved favorable changes in myostatin and follistatin levels that increase muscle mass and strength. Third, Nogueira and colleagues randomized 25 mice into one of four groups for 15 days: Group 1: Water alone; Group 2: Water plus exercise; Group 3: cocoa-derived epicatechin alone; Group 4: cocoa-derived epicatechin plus exercise (23). The groups receiving epicatechin had greater increases in skeletal muscle capillary density, TFAM quantity, mitochondrial cristae abundance, treadmill running ability, and mitochondrial activity, compared to mice receiving water alone (23). Groups receiving epicatechin also had less muscle fatigue. In summary, preclinical evidence shows that epicatechin, the major flavanol

component of cocoa, increases mitochondrial biogenesis, mitochondrial function, and capillary density in skeletal muscle. Epicatechin improves muscle strength and running capacity in animals.

C. Preliminary evidence from humans without PAD suggests that epicatechin-rich cocoa improves mitochondrial function, increases muscle mass, and improves strength. Taub and colleagues administered chocolate squares and cocoa beverages daily for three months to five patients with type 2 diabetes and heart failure (age 41 to 71 years) (25). Total daily epicatechin content in the cocoa products was 100 mgs. In thigh muscle biopsies, nitric oxide, PGC-1 α , TFAM, and mitochondrial cristae volume all increased following cocoa treatment. In a separate uncontrolled trial, Gutierrez-Salmean administered cocoa-derived epicatechin to 6 healthy young people (mean age 28.5 years) and 6 older healthy people (mean age 62) (22). Plasma levels of myostatin decreased, follistatin increased, and grip strength improved following epicatechin treatment. These preliminary studies in humans support our hypotheses that cocoa and epicatechin improve muscle mitochondrial function and biogenesis, muscle mass, and strength. However, these studies were limited by small sample sizes and lack of control groups. Further evidence is needed.

D. Dark chocolate acutely improves endothelial function and treadmill walking in PAD. Loffredo and colleagues randomized 20 PAD patients (mean age 69 years) to 40 grams of dark chocolate (>85% cocoa) vs. 40 grams of milk chocolate (<35% cocoa) in a single-blind cross-over study (31). Two hours after ingesting dark chocolate, increases were observed in treadmill walking time (124.8 + 60.8 to 142.2+62.0 seconds, P<0.001), brachial artery flow-mediated dilation (FMD) (2.3%+2.2% to 6.3%+2.7%, P<0.001), and nitric oxide (11.0 umol/L+5.8 to 17.3 umol/L+5.8, P=0.001). Milk chocolate ingestion did not affect any of these outcomes. These data demonstrate an acutely beneficial effect of dark chocolate in PAD. However, the effect of chronic daily administered dark chocolate on clinically important outcomes in PAD is unknown.

In summary, pre-clinical evidence and small human studies show that cocoa and the cocoa-derived flavanol, epicatechin, target key pathophysiologic abnormalities in people with PAD that are linked to functional impairment in PAD (21-28,31).

2.3 Scientific background and significance of research based on existing literature.

A. PAD is common and is associated with increased functional impairment and faster rates of functional decline compared to people without PAD. PAD affects 10-15% of community dwelling men and women age 60 and

older (52-54) and will be increasingly prevalent as the U.S. population survives longer with chronic disease.

B. Cocoa is the dried and fermented seed from *theobroma cacao*, from which chocolate is made (see photo to left). Epicatechins are flavanols, a major ingredient of cocoa, that have therapeutic effects on skeletal muscle and the vasculature (21-30). In pre-clinical models, cocoa and/or its major flavanol, epicatechin, promote skeletal muscle mitochondrial biogenesis, increase capillary growth, improve endothelial function, and reduce ischemia/perfusion injury (21-24). Cocoa and/or its major flavanol, epicatechin, also increase muscle mass and strength by favorably altering skeletal muscle levels of follistatin and myostatin (21,23,25). Pathophysiologic impairments in PAD that can be targeted by favorable effects of epicatechin-enriched cocoa are described below.

Innovation of the research.

A. Cocoa therapy has never been studied as a chronic, daily therapy for PAD. Patients with PAD have reduced calf muscle mitochondrial energy production, reduced calf muscle mass and strength, and impaired endothelial function (13-20,40,41). Cocoa and epicatechin improve mitochondrial energy production, increase mitochondrial biogenesis, increase skeletal muscle mass and strength, and improve endothelial function (11-20). Thus, chronic, daily epicatechin-rich cocoa has the potential for benefit in PAD.

B. The COCOA-PAD Study will measure the effects of chronic daily epicatechin-rich cocoa on changes in calf muscle biopsy measures and endothelial function in PAD. Calf muscle biopsies and brachial artery FMD at baseline and follow-up will delineate biologic pathways associated with improved walking performance in PAD. Our calf skeletal muscle measures of TFAM, follistatin, and myostatin have never been studied before in people with PAD.

C. The study of therapeutic properties of a food-derived product is innovative. This study has potential for far-reaching implications, since cocoa is widely accessible and acceptable to people with PAD. If the hypotheses of our proposed pilot trial are correct, a large definitive trial will be warranted.

Justification for proposed dose.

Our intervention is a dark cocoa beverage, naturally rich in epicatechin, manufactured by The Hershey Company. Previous human study suggests that approximately 70 to 100 mgs of epicatechin per day is optimal for improving skeletal muscle mitochondrial biogenesis, mitochondrial function, and strength (22,25). For example, in the study by Taub et al

described in section A16 (25), the cocoa intervention contained 100 mgs of epicatechin. We will prescribe three servings per day of the epicatechin-rich cocoa beverage, providing 75 mg daily of epicatechin. The Hershey's Company also produces a cocoa-free placebo drink that is packaged identically and appears and tastes identically to the cocoa beverage and has nearly identical nutritional content, including calories. Each beverage (cocoa and placebo) is prepared by dissolving the contents of a packet into water. Participants will be asked to drink three beverages per day.

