9.0 Procedures Involved

9.1 Study design.

Telephone screening.

Initial eligibility criteria will be assessed by telephone via a telephone call script. The study will be described to the potential participant and the participant will be asked a series of eligibility questions to determine whether they qualify for a baseline study visit. If they qualify for a baseline visit, we will collect their name, address, telephone number(s), e-mail address, date of birth, gender, race, and ethnicity.

In addition, some participants may be asked questions about their interest in supervised treadmill exercise programs, barriers to their participation in supervised exercise programs, and their ability to participate in supervised treadmill exercise programs. These additional questions will be collected as pilot data for a subsequent study and may be administered at any time point during the COCOA-PAD trial.

Baseline testing.

Participants will be asked to come to Northwestern Memorial Hospital at baseline for the purposes of providing informed consent. In addition, at the baseline study visits, we will obtain the ankle brachial index (ABI) measurement, to ensure they are eligible for the study. We will administer study questionnaires to obtain information about medical history, including presence of comorbidities, medication use, smoking status, and other health characteristics. We will perform baseline physical functioning tests including the six-minute walk test, chair stands, balance testing, and the treadmill walking performance test. We will take a blood sample, measure participants' height and weight, and measure the blood pressure in their arm. We will perform a test of brachial artery flow-mediated dilation (FMD). Physical activity levels will be measured using an accelerometer. In addition, participants will be asked to undergo an MRI and a calf muscle biopsy at baseline. However, potential participants not eligible for MRI testing will still be allowed to participate. Participation in the calf muscle biopsy is optional. Baseline study visits will be performed over multiple days. Participants who have a muscle biopsy will be telephoned at approximately seven days after the muscle biopsy. Participants who report any complaints about their biopsy site (such as significant pain or redness) will be scheduled for an evaluation of their biopsy site by a study physician.

Details of baseline visit procedures are described in section 9.2.

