11.0 Data and Specimen Management

11.1 Data management.

Data is recorded using preprogrammed instruments and an electronic case report form using secure, HIPAA-compliant REDCap database software on servers maintained by Northwestern's Clinical and Translational Sciences Institute. We have substantial experience with REDCap.

11.2 Power Estimates/Calculations.

The COCOA-PAD Study is a pilot study intended to collect preliminary data to estimate an effect size and to assess the feasibility of our proposed methods. Therefore, we calculated the sample size that allows us to identify an effect size estimate. Our power calculations anticipate a < 10% drop-out rate at 6-month follow-up, based on data from our completed GOALS and SILC randomized trials in PAD participants (34,60). For our primary aim, we will compare changes in six-minute walk performance at 6-month follow-up between the epicatechin-rich cocoa group and the placebo group. Comparisons will be made for measures obtained both while off of the study beverages for 2.5 hours and while off of the study beverages for 24 hours, respectively, in order to assess both acute and chronic effects of cocoa on six-minute walk. A total of 40 participants completing the trial will provide a two-sided 95% confidence interval (CI) with a margin of error of 0.64 standard deviation (SD) for the effect size in change of six-minute walk performance between the cocoa (n=20) and the placebo groups (n=20). Using the estimated SD from our SILC trial (34), the margin of error of 0.64 SD represents approximately 33 meters. Prior studies have defined clinically meaningful changes in the six-minute walk as 20 meters (small meaningful difference) and 50 meters (large meaningful difference) (73,74). Similarly, 40 participants completing the trial provides a two-sided 95% CI with a margin of error of 0.64 SD for the effect size in 6-month change of each secondary outcome between the cocoa and placebo groups.

Statistical Analyses. Data will be analyzed according to each participant's originally assigned group, irrespective of whether the participant adheres to his/her assigned group (i.e. intention to treat principle). For our Primary Aim, we will use a t-distribution to obtain the 95% CI for the difference in changes in six-minute walk performance at 6-month follow-up between the

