23.0 Local Number of Subjects

We will identify and randomize 44 eligible participants.

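### The exploratory mechanism correlations use the cocoa arm only; without the placebo arm as reference they cannot by themselves support a cocoa pathway, and this analysis leaves out about half the planned pairs

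*Combined protocol and SAP*

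**What the plan says.** Section 1.1, Exploratory Aims, sets both the population and the statistic. The population is cocoa participants only: "Among participants with PAD age 60 and older randomized to epicatechin-rich cocoa, we will determine whether the degree of improvement" in six-minute walk and in treadmill performance "is correlated with the degree of improvement in a) calf skeletal muscle perfusion; b) calf skeletal muscle measures of" regeneration and, third, of oxidative stress. The four secondary aims in the same section are all comparisons with placebo; this aim has no comparator.

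The placebo pairs are planned. Section 9.1 repeats every baseline test at six months without distinguishing the arms. The MRI paragraph of section 9.2 describes perfusion change in cocoa versus placebo. Secondary aims 3 and 4 compare perfusion, regeneration and oxidative stress between arms.

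Not everyone will contribute a pair. Section 9.1 states "Participation in the calf muscle biopsy is optional", and it admits patients who cannot have MRI.

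The Statistical Analyses text in section 11.2 gives methods for the primary and secondary aims only. It contains no placebo-arm correlation, arm-by-change interaction or mediation analysis. Section 2.3, under Innovation of the research, states the wider purpose: "Calf muscle biopsies and brachial artery FMD at baseline and follow-up will delineate biologic pathways associated with improved walking performance in PAD".

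**The concern.** A correlation between two changes within one treated group has two possible sources: a treatment effect that varies between patients and runs through the measure, or ordinary covariation of change that would occur anyway (intercurrent illness, a change in activity, season). The placebo arm shows how large the second source is. With the cocoa arm alone the two cannot be told apart.

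The protocol's own background makes some natural covariation plausible. Section 2.2 reports that worse calf muscle characteristics and lower ATP production go with worse function in PAD. Those findings are not correlations of change with change, so they do not supply a value.

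What is at stake is interpretation. Section 11.3 says that the decision on a larger trial will rest on all the pilot's evidence taken together. A cocoa-arm correlation could enter that judgement as mechanistic support when it carries no information about cocoa. The restriction also costs precision in a study that is already small.

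**Working it through.** **Inputs from the documents.** Section 23.0: "We will identify and randomize 44 eligible participants". Section 11.2: "Our power calculations anticipate a < 10% drop-out rate at 6-month follow-up", and 20 completers per arm. At exactly 10% drop-out, 44 × 0.90 = 39.6, or about 40. The aim names seven measures: perfusion (1), regeneration (4: satellite cell number, activation state, centrally nucleated fibers, embryonic myosin fibers) and oxidative stress (2). Six of the seven need the biopsy.

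**The plan's own precision figure.** The margin for a between-arm difference is t(0.975, 38 df) × √(1/20 + 1/20) = 2.024 × 0.3162 = 0.640 SD. This reproduces the stated 0.64 SD. No precision figure is given for the correlations.

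**Share of pairs used.** 20 / 40 = one half of expected completers, before losses to missing biopsy or MRI.

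**How often a cocoa-only correlation is significant when cocoa does nothing.** Assumption: the change-change correlation ρ is the same in both arms, with no cocoa effect. At n=20 the critical |r| for two-sided 0.05 is 0.444. Simulated rates:

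| Natural ρ (assumed) | Significant, two-sided 0.05 |
|---|---|
| 0 | 5% |
| 0.2 | about 14% |
| 0.3 | 25% |
| 0.4 | 43% |
| 0.5 | 64% |

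For ρ above 0 these rates are power to detect a real association; they are not error rates for the question the aim asks. Under the same assumption, a between-arm comparison of the correlations stays at about 5% for every ρ tried (0, 0.3, 0.5 and 0.7).

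**Precision with and without placebo.** Fisher z, taking r = 0.4 as an example, with atanh(0.4) = 0.424:

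- Cocoa only, n=20: SE = 1/√17 = 0.243; 0.424 ± 0.475 gives a 95% CI of −0.05 to 0.72.
- Both arms adjusted for arm, N=40: SE = 1/√(40−4) = 0.167; 0.424 ± 0.327 gives 0.10 to 0.64.
- If only 10 per arm have pairs (assumption), cocoa only: SE = 1/√7 = 0.378; the CI is −0.31 to 0.82.
- The same 10 per arm, both arms, N=20: SE = 1/√16 = 0.25; the CI is −0.07 to 0.72.

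Adjusting for baseline values as well costs a little more. With two baseline covariates at N=40, SE = 1/√34 and the interval is 0.09 to 0.64.

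**Why pooling must adjust for arm.** If cocoa shifts both changes by 1 SD and there is no link within either arm (assumption), the unadjusted pooled correlation averages about 0.20. It is significant at two-sided 0.05 in 24% of simulated trials.

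**What the interaction can deliver.** The SE of the difference in z is √(2/17) = 0.343. For r = 0.5 in cocoa against 0 in placebo, 0.549/0.343 = 1.60, so power at two-sided 0.05 is Φ(1.60 − 1.96) = 36%. For 0.7 against 0 it is 72%.

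**The case against.** The strongest reply is that the aim is labelled exploratory and asks only whether improvements are correlated among cocoa participants. A within-arm correlation answers that question. No test level, pathway claim or decision rule is attached. All five hypotheses in section 1.2 are comparisons with placebo, and secondary aims 3 and 4 already test whether cocoa changes each of these measures. This stands, and it limits the point to what a positive correlation may be taken to show.

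Several stronger readings are tempting, and the documents do not support them:

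- *A positive correlation is to be expected even if cocoa does nothing.* It can arise. How often depends on a natural correlation that is not given; at zero the rate is the nominal 5%.
- *The one-sided 0.10 level applies, which makes the rates higher.* Section 11.3 spells that level out through between-group differences, and no level is assigned to the correlations.
- *The pathway sentence in section 2.3 justifies the MRI.* It names biopsies and FMD, not MRI, and FMD is not among the exploratory correlations.
- *Half the data are thrown away.* The placebo data serve the randomized comparisons; only this analysis omits them.
- *Twenty pairs is the ceiling.* Twenty is the planned completer count per arm; about 22 per arm are randomized.
- *Using both arms would settle mechanism.* Change in the measure is not randomized, and a real pathway could have the same slope in both arms.

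It is also fair to say that the precision gain is modest if biopsy uptake is low: with 10 pairs per arm, the both-arm interval for r = 0.4 still includes zero.

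**Conclusion.** The point holds in limited form. The restriction to cocoa is explicit, paired placebo measures are planned, and nothing in section 11 supplies a reference for ordinary covariation. A cocoa-arm correlation alone therefore cannot support a cocoa pathway.

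The size is conditional: about 14% to 64% at two-sided 0.05 with n=20, if the natural correlation is 0.2 to 0.5, the same in both arms, and cocoa has no effect. About half the expected pairs go unused in this analysis; the actual number is unknown because biopsy and MRI uptake are not stated. The primary and secondary comparisons are unaffected. This is an inexpensive improvement to an exploratory analysis, worth making before the correlations are interpreted.

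**What to change.** Replace the cocoa-only correlations with one model per measure and walking outcome, in all participants with paired data: change in walking on change in the measure, arm, and the baseline values of both. Keep arm in the model so that a shift in both means does not create a pooled correlation.

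Report each arm's correlation with its confidence interval and number of pairs side by side, and give the arm-by-change interaction as descriptive. Call the results associations. Discuss a possible pathway only for measures on which the planned between-arm comparison (secondary aims 3 and 4) also shows a difference, and state that this does not prove mediation.

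The cost is a change of wording in the analysis plan; no new data or procedures are needed. The interaction will be imprecise, and the precision gain shrinks if few participants have paired biopsies. The report should say so.
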